19.11. Primary Efficacy Objective

Subjects Included the Analysis: Subjects who meet the ITT definition.

Efficacy: Primary patency of stented segment (confirmed by core laboratory) at 12 months evaluated per subject.

Hypothesis:

H_0 : Proportion of subjects with primary patency (p_{p_pat}) is less than or equal to performance goal (PG) at 12 months, $p_{p_pat} \leq PG$

H_1 : Proportion of subjects with primary patency is greater than the performance goal at 12 months, $p_{p_pat} > PG$

The primary patency proportion will be calculated such that the numerator is the number of subjects found to be patent at 12 months. The denominator is the total number of subjects found to be patent or not patent at 12 months.

Patency is:

- An in-window patent stenosis assessment with no reintervention per definition prior to the close of the 12-month window.
- In the absence of an in-window stenosis assessment, a subsequent patent stenosis assessment with no prior reintervention per definition can be used to declare patency at 12 months.

Lack of patency is:

- A reintervention per definition prior to the close of the 12-month visit window.
- A non-patent stenosis assessment within the 12-month visit window.

Performance Goal: The PG for primary efficacy will be set when all enrolled subjects complete the index procedure of this pivotal IDE trial based upon the proportions of ITT subjects in each of the disease states, i.e. nonthrombotic (p_{NT_ENROLL}), acute thrombotic (p_{AT_ENROLL}) and chronic postthrombotic (p_{CPT_ENROLL}). The disease state specific PGs were adopted as suggested in Razavi et al¹ that is, the lower 95% confidence limit minus 0.10. The disease state PGs are .83, .70 and .66 for nonthrombotic, acute thrombotic and chronic postthrombotic subjects respectively. The PG for the

pivotal study will be a weighted combination of these disease state specific PGs, where the weights are the proportion of subjects in each disease state in the ITT sample, i.e. study PG = $(p_{NT_ENROLL}) * 0.83 + (p_{AT_ENROLL}) * .70 + (p_{CPT_ENROLL}) * 0.66$. The same PG will be used overall and in the SARS-CoV-2 negative subgroup. In order to have a minimum number of subjects from each disease condition in the ITT sample, the study will require that at least 20% of the ITT subjects are in each of the disease state.

Sample Size Rationale: With an expected FAS sample size of N=128, one-sided Type I error less than or equal to 2.5%, and assumed primary patency at 12 months equal to .96, .87, .79, i.e. the point estimates for primary patency from Razavi et al for nonthrombotic, acute thrombotic, and chronic postthrombotic respectively, the power for primary efficacy ranges from 96 – 99% depending on proportion in each disease-state given a minimum of at least 20% in each group. The table below provides the matrix of simulated power varying the ITT proportions for the disease states.

Power Calculations Using Simulation for the Primary Statistical Analysis

Proportion of Subjects Expected in Each Group			Assumed Freedom from Primary Efficacy				Calculated Performance Goal				Power at N=128 Evaluable (20% attrition for N=160 enrolled)
NT	AT	CPT	NT	AT	CPT	Pooled	NT	AT	CPT	PG	One-sided Type I error = 2.5%
0.3333	0.3333	0.3333	0.96	0.87	0.79	0.873	0.83	0.7	0.66	0.73	98%
0.2	0.2	0.6	0.96	0.87	0.79	0.84	0.83	0.7	0.66	0.702	96%
0.2	0.6	0.2	0.96	0.87	0.79	0.872	0.83	0.7	0.66	0.718	99%
0.6	0.2	0.2	0.96	0.87	0.79	0.908	0.83	0.7	0.66	0.77	96%
0.3	0.3	0.4	0.96	0.87	0.79	0.865	0.83	0.7	0.66	0.723	97%
0.3	0.4	0.3	0.96	0.87	0.79	0.873	0.83	0.7	0.66	0.727	99%
0.4	0.3	0.3	0.96	0.87	0.79	0.882	0.83	0.7	0.66	0.74	98%
0.4	0.4	0.2	0.96	0.87	0.79	0.89	0.83	0.7	0.66	0.744	99%
0.4	0.2	0.4	0.96	0.87	0.79	0.874	0.83	0.7	0.66	0.736	98%
0.2	0.4	0.4	0.96	0.87	0.79	0.856	0.83	0.7	0.66	0.71	98%

Primary Statistical Analysis: The primary statistical analysis will be conducted in the FAS subjects overall and in the SARS-CoV-2 negative subgroup. The primary statistical comparison will use a one-sample Z-test comparing the proportion of subjects with primary patency to the PG using a one-sided $\alpha = 0.025$ equivalent to a z-score of 1.96. The variation in the proportion will be estimated using the disease-specific performance goals themselves, i.e. under the null, rather than use the estimated patency rates, i.e. under the alternative.

The estimates that will be observed for primary patency in each disease etiology are noted as follows:

$\hat{p}_{p_pat_NT}$ = The primary patency observed in the NT subjects.
 $\hat{p}_{p_pat_AT}$ = The primary patency observed in the AT subjects.
 $\hat{p}_{p_pat_CPT}$ = The primary patency observed in the CPT subjects.

The percent of subjects in the FAS with each disease etiology are noted as follows:

p_{NT_FAS} = The proportion of FAS subjects with NT disease etiology.
 p_{AT_FAS} = The proportion of FAS subjects with AT disease etiology.
 p_{CPT_FAS} = The proportion of FAS subjects with CPT disease etiology.

The number of subjects in the FAS set with each disease etiology are noted as follows:

n_{NT_FAS} = The number of FAS subjects with NT disease etiology.
 n_{AT_FAS} = The number of FAS subjects with AT disease etiology.
 n_{CPT_FAS} = The number of FAS subjects with CPT disease etiology.

The primary patency for the hypothesis test is calculated as:

$$p_{p_pat} = p_{NT_FAS} * \hat{p}_{p_pat_NT} + p_{AT_FAS} * \hat{p}_{p_pat_AT} + p_{CPT_FAS} * \hat{p}_{p_pat_CPT}$$

with the variance of primary patency calculated as follows:

$$\text{var}(p_{p_pat}) = ((p_{NT_FAS})^2 PG_{NT}(1 - PG_{NT}))/ n_{NT_FAS} + ((p_{AT_FAS})^2 PG_{AT}(1 - PG_{AT}))/ n_{AT_FAS} + ((p_{CPT_FAS})^2 PG_{CPT}(1 - PG_{CPT}))/ n_{CPT_FAS}$$

Such that the Z score is calculated as follows:

$$Z = (p_{p_pat} - PG) / \text{square root}(\text{var}(p_{p_pat}))$$

When $Z > 1.96$, the primary patency is found to be significantly greater than the performance goal with two-sided Type I error held at 5%, i.e. two-sided p-value < 0.05 .

The two-sided p-value in the SARS-CoV-2 negative subgroup and all subjects will be calculated and ordered from largest to smallest. If the largest p-value, is statistically significant at $p < 0.05$ then the

hypothesis test is statistically significant in both the SARS-CoV-2 negative subset and all subjects. If not, testing continues to the smallest p-value. If the smallest p-value < 0.025 then the hypothesis test is statistically significant in the group for which the smallest p-value is associated with. If the smallest p-value ≥ 0.025 , then the hypothesis test is not statistically significant in either the SARS-CoV-2 negative subset nor all subjects.

Additional Analysis: As a supportive analysis to the primary patency analysis, a Kaplan-Meier analysis will also be performed using the patency data overall and in the SARS-CoV-2 negative subset. Time 0 is the index procedure and the event is lack of patency based on 1) reintervention per definition 2) a non-patent stenosis assessment within the 12 month visit window. For subjects who do not experience an event, the time of censoring is the date of the last follow-up whether scheduled or unscheduled.

The evaluation for pooling analyses specified in **Section 19.6** will be completed. If there is missing data for the ITT subjects, the sensitivity to missing data analysis outlined in **Section 19.7** will be completed. Additionally, the primary statistical analysis will be conducted in the per protocol sample overall and in the SARS-CoV-2 negative subset.

19.12. **Subgroup Summaries for Primary Endpoints**

Summary statistics for the following subgroups will be summarized. The study was not powered to demonstrate the primary efficacy and safety endpoints within the subgroups and therefore it is not an expectation that the primary safety and efficacy endpoint will be statistically significant within the subgroups defined by disease etiologies (NT, AT, CPT), gender, age, race and ethnicity. Age subgroups are defined by dichotomizing at the median.

19.13. **Secondary and Observational Endpoints**

The secondary endpoints are listed in **Section 6.2** and the observational endpoints are listed in **Section 6.3** and are supportive in nature. Descriptive statistics will be calculated and may be provided in labeling if deemed informative for the user. Descriptive statistics for the purposes of labeling are defined as N, mean, standard deviation, median, interquartile range, minimum and maximum for continuous variables, and number and percent of observations for categorical variables.

Standard statistical methods will be used and include the Kaplan-Meier product limit method for time to event endpoints and the Wilcoxon signed rank test for changes from baseline for endpoints compared to baseline. Statistical significance will be defined as two-sided $\alpha < 0.05$. Two-sided 95% confidence intervals may be calculated for estimates. P-values and 95% confidence intervals are not intended for the labeling.

Safety and efficacy endpoints will be evaluated in the sample of subjects meeting the ITT and PP definition in both the SARS-CoV-2 negative subgroup and all subjects.

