19.3. Enrollment Sample Size

The maximum sample size for primary safety and efficacy is that of primary safety or 140 subjects required at 30 days. Conservatively, correcting that number for approximately 12.5% attrition at 30 days requires enrollment of 160 subjects. With 160 subjects enrolled and accounting for 20% attrition by 1 year, it is expected that 128 subjects will be evaluable for primary efficacy at 1 year providing 96 to 99% power depending on the proportion enrolled in each disease state.

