H₁: Proportion of subjects with freedom from MAE is greater than the (PG) at 30 days, $p_{MAE} > 89\%$

The freedom from MAE proportion will be calculated such that the numerator is the number of subjects in whom a MAE did not occur within 30 days of the index procedure. The denominator is the number of subjects with 30 days of follow-up plus the number of subjects with a MAE prior to 30 days who exited the study prior to 30 days, if any.

Sample Size Rationale: Using PASS 19, a one-sample Exact Test (binomial enumeration), power = 90%, one-sided Type I error controlled at 2.5%, and assumed freedom from MAE of 96.1% with a PG goal of 89%, the required evaluable sample size is 140 subjects.

Primary Statistical Analysis: The primary statistical analysis will be conducted in the FAS subset for the primary safety endpoint overall and in the SARS-CoV-2 negative subset. The primary statistical method is a one-sample exact test comparing the proportion of subjects free from a MAE to the PG using a two-sided $\alpha = 0.05$. The exact two-sided 95% confidence interval for the proportion of subjects free from MAE will be calculated.

The two-sided p-value in the SARS-CoV-2 negative subgroup and all subjects will be calculated and ordered from largest to smallest. If the largest p-value, is statistically significant at $p < 0.05$ then the hypothesis test is statistically significant in both the SARS-CoV-2 negative subset and all subjects. If not, testing continues to the smallest p-value. If the smallest p-value < 0.025 then the hypothesis test is statistically significant in the group for which the smallest p-value is associated with. If the

¹ Razavi MK, Jaff MR, Miller LE. Safety and Effectiveness of Stent Placement for Iliofemoral Venous Outflow Obstruction Systematic Review and Meta-Analysis. Circ Cardiovasc Interv. 2015;8:e002772. DOI: 10.1161/CIRCINTERVENTIONS.115.002772.)

smallest p-value ≥ 0.025 , then the hypothesis test is not statistically significant in either the SARS-CoV-2 negative subset nor all subjects.

Additional Analysis: The evaluation for pooling analyses specified in **Section 19.6** will be completed. If there is missing data for the ITT subjects, the sensitivity to missing data analysis outlined in **Section 19.7** will be completed. Additionally, the primary statistical analysis will be conducted in the per protocol sample overall and in the SARS-CoV-2 negative subset.

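### Whether a subject enters either primary proportion depends on the outcome: stated safety power is overstated at the plan's own attrition, and the direction of the efficacy bias is left open

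*Combined protocol and SAP*

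**What the plan says.** **Safety (Section 19.10).** For the proportion, "the numerator is the number of subjects in whom a MAE did not occur within 30 days of the index procedure". To those followed to day 30, the denominator adds a second group: "plus the number of subjects with a MAE prior to 30 days who exited the study prior to 30 days, if any". An early exiter is therefore counted if she had an MAE and omitted if she did not. The sample size uses a "one-sample Exact Test (binomial enumeration), power = 90%, one-sided Type I error controlled at 2.5"%, with "assumed freedom from MAE of 96.1% with a PG goal of 89%, the required evaluable sample size is 140 subjects". Section 19.3 divides 140 by one minus 12.5% attrition to reach 160 enrolled, and calls this conservative.

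**Efficacy (Section 19.11).** "The denominator is the total number of subjects found to be patent or not patent at 12 months". Lack of patency is either "A reintervention per definition prior to the close of the 12-month visit window" or a non-patent assessment inside that window. Patency needs an in-window patent assessment. If there is none, a later patent assessment with no earlier qualifying reintervention will do. No rule covers a later non-patent assessment, or a non-patent scan before the window that led to no reintervention. On numbers, "accounting for 20% attrition by 1 year, it is expected that 128 subjects will be evaluable for primary efficacy", and Section 19.11 gives 96–99% power at 128 across ten disease-state mixes.

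**Supporting analyses.** Section 19.7 plans best-case, worst-case and tipping-point imputation in the ITT sample for both endpoints. Section 19.11 adds a supportive Kaplan-Meier analysis of patency, censored at the last follow-up of any kind. Section 19.10 names no Kaplan-Meier analysis for 30-day safety.

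**The concern.** A proportion estimates the rate in the enrolled population only if membership of its denominator does not depend on the result. Here it does, in two ways.

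- **Early exit.** Recorded failures are collected from everyone enrolled, but successes only from those who stay. This lowers both rates.
- **Late scans (efficacy only).** Among subjects who miss the 12-month window, later successes are let in and later failures are not. This raises the patency rate.

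The power statements treat attrition as removing successes and failures in equal proportion. For safety, the endpoint that sets the enrolment figure, a device performing exactly as assumed would miss its goal more often than the plan says. For efficacy, the late-scan rule could let a device at the performance goal (PG) pass more often than 2.5% of the time.

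**Working it through.** **Inputs from the documents.** Safety: 160 enrolled, 140 evaluable, assumed rate 96.1%, PG 89%. Efficacy: 20% attrition, assumed patency .96/.87/.79, PGs .83/.70/.66, null-variance Z-test at 1.96.

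**Assumptions not in the documents.** Exit or a missed window is unrelated to outcome. *c* is the share of failures among exiters (for efficacy, among those missing the window) that is recorded and so retained; for efficacy only reinterventions qualify. *g* is the share of patent subjects missing the window who have a later patent scan. Ranges are shown for both. Each test is taken alone, in all subjects, without the Hochberg step.

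**Safety: the plan's figure.** At n = 140 the exact one-sided 2.5% test allows at most 8 MAEs: P(Bin(140, .11) ≤ 8) = 0.024. Power is P(Bin(140, .039) ≤ 8) = 0.902. The stated 90% reproduces.

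**Safety: the written denominator.** With 20 exiters, expected rate = .961 × 140 / (140 + 20 × .039 × c). At c = 1 this is 134.54 / 140.78 = 0.9557, a bias of −0.5 points; at c = 0.5 it is 0.9583. The allowance stays at 8 MAEs until n reaches 152, so nearly every retained exiter MAE uses up allowance without adding any. Exact power, with the limit recomputed at each realised n:

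| Exits of 160 | c = 0 | 0.25 | 0.5 | 0.75 | 1 |
|---|---|---|---|---|---|
| 20 (12.5%) | 90.2% | 88.5% | 86.6% | 84.7% | 82.5% |
| 8 | 92.5% | 92.0% | 91.4% | 90.9% | 90.3% |
| 4 | 91.4% | 91.2% | 90.9% | 90.6% | 90.3% |

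Power does not move smoothly with the number of exits because the exact limit steps from 8 to 9 at n = 152. With 12 exits, for example, it is 87% even at c = 0.

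**Efficacy: the plan's figures.** Simulating the Section 19.11 test at 128 evaluable reproduces nine of the ten tabulated powers within 2 points. The 0.6/0.2/0.2 row is printed as 96% and computes to about 99.5%, a separate matter.

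**Efficacy: the written rules.** With a = 0.20 missing the window and true pooled patency p, approximately

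E = p(1 − a + a·g) / [p(1 − a + a·g) + (1 − p)(1 − a + a·c)].

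Equal thirds, p = 0.873, PG = 0.73:

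| c | g | Expected estimate | Power |
|---|---|---|---|
| 0 | 0 | 0.873 | 98.6% |
| 0.25 | 0 | .6987/.8063 = 0.866 | 97.6% |
| 0.5 | 0 | .6987/.8127 = 0.860 | 96.0% |
| 1 | 0 | .6987/.8253 = 0.847 | 90.8% |
| 0.5 | 0.5 | .7860/.9000 = 0.873 | 99.3% |
| 0 | 0.5 | .7860/.8873 = 0.886 | 99.9% |

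The two effects cancel when g = c. With true rates at the PGs, c = 0 and g = 0.5, the expected estimate is .657/.873 = 0.753 against 0.730, and simulated one-sided rejection is about 8%. At c = 0.25 and g = 0.5 it is 4.4%. With c = 0.5 and g = 0 it falls to about 0.5%, so the early-exit effect alone is conservative.

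**The case against.** **The plan already has protection.** Section 19.7 imputes every missing ITT subject, so its best-case and worst-case runs do not select on outcome and they bound the answer for both endpoints. Section 19.11 also plans a patency Kaplan-Meier analysis. A reader might infer that nothing in the plan addresses early exit; that would be wrong. These analyses are supportive, however. They alter neither the primary ratios nor the power statements. The Kaplan-Meier analysis is not specified by disease state or compared with the PG.

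**The safety effect is small and conservative.** This stands: the bias is at most about 0.5 points and makes false success less likely. Section 19.3 calls 12.5% conservative, and Section 15.7 does not allow a subject to be declared lost to follow-up before the 12-month window has passed, so 20 exits by day 30 may well not occur. With 4 or 8 exits power stays at or above 90%. Still, 12.5% is the figure used to justify 160 subjects, and 90% is not delivered there once exiters' MAEs are captured.

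**Both rates are biased downward.** A reader might infer this from the early-exit rule. The documents support it for safety only. In Section 19.11 the late-scan rule and the in-window restriction on non-patent scans push the other way, and nothing stated fixes the balance.

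**Efficacy power is really about 80%.** The 0.2/0.2/0.6 mix gives about 80% at c = 1 and g = 0. That requires every failure among subjects missing the window to have been a recorded qualifying reintervention, with no late scans at all. At c = 0.5 and g = 0 power is still about 90% in that mix, so the extreme should not be quoted as the trial's power.

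**Conclusion.** The point holds in this form. Inclusion in both primary proportions depends on outcome.

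- **Safety.** If exit is unrelated to outcome, the rate is biased slightly downward. At 20 exits of 160, the stated 90% power is about 83–88% for capture shares from 1 down to 0.25. It is 90% only if no exiter's MAE is captured.
- **Efficacy.** The direction is undetermined. At 20% missing and equal thirds, the expected estimate runs from about 0.847 (c = 1, g = 0) to 0.886 (c = 0, g = 0.5) against a true 0.873. In the second case null rejection is about 8%. The upward case matters more, because it is the one that inflates type I error.

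The sizes rest on assumed values of c and g and on non-informative exit. The existence of the two selection rules does not; it is in the text. The documents do not support calling the efficacy result biased in either direction, or giving one corrected efficacy power.

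**What to change.** 1. **Power.** In Sections 19.3 and 19.10, restate safety power under the written denominator as a range over the assumed capture share. In Section 19.11, note that 96–99% assumes attrition unrelated to outcome.
2. **Late scans.** In Section 19.11, apply one rule whatever the scan shows. If a later patent scan can stand in for a missed 12-month scan, a later non-patent scan must also be classified; otherwise use neither. Classifying late non-patent scans as failures would count some failures that began after month 12. Using neither loses some evaluable subjects.
3. **Sensitivity analyses.** Keep the exact test and the Z-test as primary. Add a 30-day product-limit estimate of freedom from MAE, with event-free exiters censored at last contact. Specify the existing patency Kaplan-Meier analysis by disease state, combined with the same weights, compared with the PG, and censored at last evaluable imaging.

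**Cost.** Changes to the wording and a little more analysis of data already collected, with no more subjects. The stated safety power becomes less favourable. The product-limit estimates rely on non-informative exit, which the Section 19.7 runs already probe.

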⁴ If a SARS-CoV-2 test is unavailable due to institution policy, a test shortage, or if there is a delay in test results, the subject must complete the COVID-19 questionnaire and answer NO to all questions to be eligible for study treatment. If a SARS-CoV-2 test is unavailable due to institution policy or a test shortage at the time of any follow-up or unscheduled visits, the COVID-19 questionnaire must be completed. A SARS-CoV-2 test will not be required if a subject has received a complete cycle of an authorized COVID-19 vaccine or has documented evidence of a positive COVID-19 antibody test, is asymptomatic, and has no long-lasting effects (per PI discretion) from a prior COVID-19 infection.

⁵ PT/INR to be obtained only if a subject is on chronic warfarin therapy.

⁶ aPTT to be obtained only if a subject is on chronic heparin therapy.

⁷ Negative urine or blood pregnancy test is required for female subjects of childbearing potential within 7 days of the index procedure.

⁸ All scheduled DUS exams should be performed per the protocol established by the core laboratory. If a DUS is non-diagnostic (per the imaging protocol), the site should make every effort to obtain a repeat exam within the visit window.

⁹ Unscheduled tests and assessments should be completed prior to any interventional procedures to target limb.

¹⁰ Unscheduled tests and assessments to be performed as clinically indicated.

¹¹ All imaging of the target limb acquired during scheduled visits or an interventional procedure to the target limb (such as venogram, IVUS, DUS, or X-ray) should be submitted to the respective core laboratory within 3 business days.

¹² Required if DUS suggests >50% stenosis or occlusion of the stented segment, or if the DUS is non-diagnostic or sub-optimal (i.e., due to obesity). If a follow-up venogram and/or IVUS is refused by the subject, this must be documented and will not be considered a protocol deviation.

¹³ For the purposes of this study, all AEs, regardless of relatedness to the study device and/or study device procedure, target limb, or underlying venous disease are required to be reported on the AE eCRF and are considered “protocol reportable”. Please see **Section 17** for more information on safety events and reporting requirements.

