15.7. Follow-up Visit Compliance

As part of the informed consent process, all reasonable efforts will be made to obtain complete data for all subjects according to the follow-up visit schedule. PI and research staff will be expected to maintain continuous and open communication with study subjects regarding their participation in this study.

Three attempts via telephone will be made to contact subjects who do not return for a study follow-up visit. If after three telephone attempts the subjects cannot be contacted, a certified letter should be sent by the PI or designated study coordinator to the subject's last known address. If possible, public records should be searched to ascertain survival status. If efforts to reach the subject are unsuccessful after three telephone contacts and a certified letter, and there is no evidence of subject expiration, or the site has not been notified of a subject's wish to withdraw consent, a protocol deviation for a visit not done must be documented in the subject's source records and reported in the EDC system. A detailed record of all contact attempts should be maintained in the subject's file. This process should be repeated for all subsequently missed follow-up visits and documented accordingly. After required contact attempts are unsuccessful for at least 2 consecutive missed follow-up visits and the 12-month visit window (or any later subsequent visit window) has passed, only then should a subject be considered lost-to-follow-up (LTFU) and exited from the study.

In the event of a public health crisis, a global pandemic, a natural disaster, or any other event which would preclude research sites from conducting research or restrict subjects' ability to attend follow-up visits, guidance will be provided by the Sponsor and may include performing follow-up visits via alternative methods, extending visit windows, etc.

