15.8. Subject Discontinuation and Replacement

A subject may discontinue participation at any time without penalty or loss of benefits to which the subject is otherwise entitled. In addition, a subject may be discontinued if in the PI's opinion it is in the subject's best interest. If a subject prematurely discontinues from the study, the reason will be recorded in the eCRF with supporting documentation. These results will be tabulated by number and percent for each category for discontinuation.

Subjects who prematurely exit the study after treatment will have their data maintained and evaluated up until the time of withdrawal. Subjects who are voluntarily or involuntarily (per PI discretion or if LTFU) withdrawn cannot re-enter the study. These subjects will not be replaced. There is no follow-up or observation planned for subjects who withdraw voluntarily or who are involuntarily withdrawn by the PI.

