17.8. Protocol Deviations and Protocol Violations

A protocol deviation occurs when, without significant consequence, the activities on a study diverge from the IRB-approved protocol. Any protocol-required test, assessment, or procedure that is not done or is done out of window is considered a protocol deviation. For example, a subject missing a protocol-required visit due to being away on vacation, or a DUS that is done out of window, would both be considered protocol deviations. All protocol deviations must be documented in EDC and reported to the Sponsor by the PI or designee upon first knowledge of the deviation.

A protocol violation is a divergence from the IRB-approved protocol that may reduce the quality or completeness of data, makes the ICF inaccurate, or impacts a subject's safety, rights, or welfare. Examples of protocol violations include, but are not limited to, the following:

- Inadequate or delinquent informed consent;
- Enrolled subject(s) who did not meet Inclusion/Exclusion criteria;
- Unreported SAEs, UADEs, SADEs;
- Multiple visits missed or visits that took place outside permissible windows;
- Materially inadequate record keeping;
- Intentional deviations from the protocol, GCP, or regulations by study personnel;
- Repeated noncompliance with study requirements;
- Events that may affect the outcome (endpoints) of the study, OR;

- Any other act or occurrence identified by the study Sponsor as constituting a violation from the protocol

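### Section 19.11 counts a post-window scan only if it is patent, so a subject with no in-window scan enters or leaves the primary efficacy analysis according to the scan result

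*Combined protocol and SAP*

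**What the plan says.** Section 19.11 gives two routes to patency. One is a patent in-window scan with no qualifying reintervention before the window closes. The other is a fallback for subjects without an in-window scan: "a subsequent patent stenosis assessment with no prior reintervention per definition can be used to declare patency at 12 months". It also gives two routes to failure: "A reintervention per definition prior to the close of the 12-month visit window" and "A non-patent stenosis assessment within the 12-month visit window". On who is counted it says: "The denominator is the total number of subjects found to be patent or not patent at 12 months".

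The fallback has no time limit, and its wording permits rather than requires its use. The 12-month window is ±30 days (15.3).

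The plan foresees scans outside the window. Section 17.8 gives as an example that "a DUS that is done out of window, would both be considered protocol deviations", although that example is not specific to month 12 and the scan could be early. For a non-diagnostic duplex scan, footnote 8 of section 8.1 says "the site should make every effort to obtain a repeat exam within the visit window". Footnote 12 and section 15.3 go further at month 12: venogram and IVUS are required if the duplex is non-diagnostic or sub-optimal, though the subject may refuse. Section 15.7 allows extended visit windows in a public health crisis or similar event.

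Subjects who withdraw cannot supply late scans (15.8: "There is no follow-up or observation planned for subjects who withdraw voluntarily"). A subject who misses only the 12-month visit can, because 15.7 declares loss to follow-up only when contact attempts are "unsuccessful for at least 2 consecutive missed follow-up visits".

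**The concern.** Take two retained subjects with no in-window scan and no qualifying reintervention. One has a patent scan after the window and counts as a success. The other has only non-patent scans after the window and is not counted at all. Whether a subject is analysed then depends on what the scan showed.

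This is a single-arm test against a fixed performance goal (PG), and study success requires the efficacy endpoint (19.4). A one-way inclusion rule could matter in a borderline result. Without a time limit, a 24-month scan could also settle 12-month patency. Because the full cohort is analysed at 12 months (19.5), such a scan would by then exist only for earlier enrollees.

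**Working it through.** **Inputs.** Disease-state PGs 0.83, 0.70, 0.66; assumed patency 0.96, 0.87, 0.79; 128 evaluable of 160; null variance from the PGs; reject if Z > 1.96 (all 19.3 and 19.11). Two quantities are not in the documents and are assumed: L, the number of late-only subjects, and r, the share of failures among unscanned subjects that appear as a qualifying reintervention before window close.

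**1. The plan's own figure.** With equal thirds, PG = (0.83 + 0.70 + 0.66)/3 = 0.73 and pooled patency is 0.873. An exact three-binomial calculation of the plan's Z-test at n = 128 gives 98.5% power, against 98% stated. The test is reproduced.

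**2. Classification when there is no in-window scan.**

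| Qualifying reintervention before window close | Later scans | Class under 19.11 |
|---|---|---|
| Yes | Any | Failure |
| No | A patent scan, no prior qualifying reintervention | Patent |
| No | Only non-patent | Neither; leaves the denominator |
| No | None | Neither; leaves the denominator |

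**3. Direction of the fallback alone.** The weights are the full-analysis-set shares, so the estimate equals x/n (patent subjects over counted subjects). Adding a late patent subjects gives (x + a)/(n + a) ≥ x/n.

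For Z, write Z = (x − n·PG)/√V, with V = Σ n_s·PG_s(1 − PG_s). One more patent subject adds 1 − PG to the numerator and at most 0.66 × 0.34 = 0.2244 to V. Z therefore rises while Z < 2(1 − PG)√V/0.2244. With equal thirds and n = 128, V = 128 × (0.1411 + 0.2100 + 0.2244)/3 = 24.55 and √V = 4.955. The bound is 2 × 0.27 × 4.955/0.2244 = 11.9. The largest possible Z is 128 × 0.27/4.955 = 7.0, so the condition always holds.

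**4. Two illustrative cases** (equal thirds, PG 0.73, no reinterventions, SE = √(0.1918/n), one population).

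| Rule | Case 1: 99/123 in window; late 4 patent, 1 not | Case 2: 95/118 in window; late 7 patent, 3 not |
|---|---|---|
| Current | 103/127 = 81.1%, Z 2.08 | 102/125 = 81.6%, Z 2.20 |
| In-window only | 99/123 = 80.5%, Z 1.90 | 95/118 = 80.5%, Z 1.86 |
| Late scans both ways | 103/128 = 80.5%, Z 1.93 | 102/128 = 79.7%, Z 1.73 |

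The two-sided p-values under the current rule are 0.037 and 0.028.

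**5. Error rate by simulation** (one population, one-sided 2.5%, equal thirds, true patency = PG, L drawn from the 128, the other 32 lost).

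| r | L = 2 | L = 5 | L = 10 |
|---|---|---|---|
| 0 | 2.3% | 3.3% | 5.2% |
| 0.25 | 1.2% | 1.4% | 2.1% |
| 0.5 | 0.5% | 0.6% | 0.8% |

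Repeat runs agree to within about 0.4 points. If L is drawn from the 32 instead, the figures are 3.0/3.2/5.0% at r = 0 and 1.3/1.6/2.7% at r = 0.25. Over the ten disease mixes of the power table, an in-window-only rule gives 1.8–2.9% at r = 0.

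The fallback's own effect on the estimate is about +0.3/+0.8/+1.6 points for L = 2/5/10. The net bias is the same at r = 0, about −1.0/−0.7/−0.1 at r = 0.25 and −2.2/−2.0/−1.6 at r = 0.5. It turns negative because unscanned subjects with a qualifying reintervention count as failures while unscanned subjects without one are dropped.

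**6. Other analyses.** In the Kaplan-Meier analysis a non-patent scan is an event only inside the window, so a late one is not an event and the subject is censored at last follow-up. In 19.7, late-only non-patent subjects are pooled with all other missing subjects. At the plan's own figures the worst case is 0.873 × 128/160 = 69.8%, already below the 73% PG, so it cannot isolate this effect.

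**The case against.** The strongest defence is that the asymmetry has a reason. A later patent scan with no prior reintervention supports patency at month 12, whereas a later non-patent scan does not date the loss. That is correct, and a reader should not infer that subjects with late non-patent scans are month-12 failures that the plan hides. But the argument supports keeping undatable scans out of the primary analysis. It does not support admitting only the favourable ones.

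Second, late-only subjects may be few, given the 12-month venogram and IVUS requirement and the extendable windows. This stands, and it limits the size of the effect.

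Third, a reader might infer that the rule inflates type I error or favours the device overall. The documents do not support that. At r = 0.25 or 0.5 in the main model the error is below 2.5%. Still, an offset of unknown size is not error control.

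Fourth, a reader might take the two cases as trial outcomes. They are not, because 19.4 applies Hochberg across all subjects and the SARS-CoV-2 negative subset. With p = 0.037 or 0.028 in all subjects, efficacy succeeds only if the subset has p < 0.05 as well (at p < 0.025 the subset succeeds by itself). Equally, Z = 1.90 in all subjects does not fail the study if the subset has p < 0.025. The cases show only that Z in one population can cross 1.96.

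Fifth, 19.7 shows some dependence on excluded subjects, but only pooled with all other missing data, and it does not change the decision.

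**Conclusion.** The point holds as a defect in the rule: among subjects with no in-window scan and no qualifying reintervention before window close, inclusion depends on the scan result. The text and the direction of the fallback's own effect are certain. The net effect is not: L and r are both assumptions, and all error and power figures are for one population without the Hochberg step. On those terms, error clearly exceeds 2.5% only when few unscanned failures are caught as reinterventions and several subjects are late-only, reaching about 5% at L = 10 and r = 0. At the design patency rates the efficacy conclusion is little affected; the exposure is a borderline result. It should be fixed before the data are seen, because the rule is easy to repair.

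**What to change.** In 19.11, make inclusion independent of the scan result:

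- Classify primary patency from in-window assessments (including any sponsor-extended window) plus qualifying reinterventions before window close.
- Move post-window scans to a sensitivity analysis that counts patent and non-patent results alike, within a short stated limit.
- State in that analysis whether a late non-patent duplex needs the same IVUS confirmation as the 12-month endpoint. Sections 8.1 (footnote 16), 9.5, 15.4 and 15.5 make IVUS at 24 and 36 months conditional on symptoms requiring reintervention, and even then not mandatory.
- Report the number of late-only subjects by result, and state how the Kaplan-Meier analysis treats a late non-patent scan.
- If late scans stay in the primary analysis, count them in both directions under the same limit and confirmation rule, and say that losses after month 12 then score as failures.

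No new data are needed. The cost is power (design rates, one population, r = 0.25, L from the 128):

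| Mix and L | Current | In-window only |
|---|---|---|
| Equal thirds, L = 5 | 98.2% | 96.7% |
| 20/20/60, L = 5 | 95.5% | 92.8% |
| 20/20/60, L = 10 | 96.5% | 90.7% |

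For the last row, counting late scans in both directions gives 94.2% with no later loss. It gives about 91.5% or 88.1% if 10% or 20% of the late-only patent subjects lose patency before the late scan. In-window only is also conservative when r > 0 (error 0.7–1.2% at r = 0.25), because the outcome-dependent inclusion that remains, through reinterventions in unscanned subjects, runs against the device.
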